13.1 Ethical Conduct of the Study / Good Clinical Practice

The conduct of this study will be consistent with the standards established by the Declaration of Helsinki and compliant with the ICH guidelines for GCP as well as with all local and / or national regulations and directives.

13.2 Source Data and Source Documents

“Source data” are the data contained in source documents. Source documents are original documents or certified copies, and include, but are not limited to, DCs, medical and hospital records, screening logs, informed consent / assent forms, telephone contact logs, and worksheets. The purpose of study source documents is to document the existence of subjects and to substantiate the integrity of the study data collected. Investigators must maintain source documents so that they are accurate, complete, legible, and up to date.

For missing or discrepant data on a DC, the study coordinator will obtain verbal clarification from the subject, enter the response into the “Investigator’s comment” page of the DC, and transfer the information to the CRB.

The subject pre-screening log should list all individuals contacted by the Investigators to participate in the study, regardless of the outcome.

The Investigator must print^a any electronic records on an ongoing basis, sign and date them immediately after creation, and keep the printouts on file as source documents that can be verified by the Sponsor or an inspector against the electronic records. Any subsequent changes of an electronic record require the record to be re-printed, dated (with an indication of the date of change), and signed. Such records must also be kept together with the original printed copy.

Good Documentation Practice should be followed by the Investigator and the site staff managing source documents.

13.3 Confidentiality of Data and Access to Subject Records

Prior to initiation of the study, the Investigator will sign a fully executed confidentiality agreement with Sanofi Pasteur.

Sanofi Pasteur personnel (or designates), the IECs / IRBs, and regulatory agencies, including the FDA, require direct access to all study records, and will treat these documents in a confidential manner.

In the event a subject's medical records are not at the investigational site, it is the responsibility of the Investigator to obtain those records if needed.

13.4 Monitoring, Auditing, and Archiving

13.4.1 Monitoring

Since monitoring tasks may be carried out by a subcontractor who is not determined at the time of protocol writing, note that, activities performed "by" the Sponsor, can be read as "under the responsibility of" the Sponsor.

Before the start of the study (ie, before the inclusion of the first subject), the Investigators and the Sponsor's staff or a representative will meet at the site-initiation visit to discuss the study protocol and the detailed study procedures. Emphasis will be placed on inclusion and exclusion criteria, visit timing, safety procedures, informed consent procedures, SAE reporting procedures, CRB completion, and the handling of samples and products. The Sponsor's staff or a representative will ensure and document that all material to be used during the study has been received at the site; and that the study Investigator team and local Sponsor/delegate staff have been properly informed about the study, GCP and regulatory requirements, and the Sponsor's procedures. Specific training sessions for the study investigator team and the CRAs on these topics may be performed as necessary, and should be documented.

The following instruction manuals will be provided: the CRF Completion Instructions for entering data into the CRB, and the Operating Guidelines for detailed study procedures such as the product management and sample-handling procedures.

^a Unless the electronic medical records are managed by validated computerized systems that are compliant with US 21 CFR Part 11, in which case they are acceptable on their own.

After the start of the study, the Sponsor's staff or a representative will be in regular contact with the investigational team through telephone calls and regular follow-up visits. The Investigator or delegate must be available for these visits, and must allow the Sponsor/delegate staff direct access to subject medical files and CRBs. During these visits, the Sponsor/delegate staff will:

- Evaluate the quality of the study progress (adherence to protocol and any study-specific guidelines, quality of data collection and document completion, signature of consent forms, occurrence of SAEs, sample and product management, cold chain monitoring, archiving)
- Source-verify completed CRBs and any corresponding answered queries
- Determine the number of complete or ongoing issues identified at monitoring visits (eg, protocol deviations, SAEs). Any identified problems will be discussed with the Investigator, and corrective or preventive actions will be determined, as appropriate.
- After all protocol procedures have been completed and the data have been entered into the CRB, the Investigator must still be available to answer any queries forwarded by the Sponsor. All data-related queries must be completed prior to database lock.

At the end of the study, a close-out visit will be performed to ensure that:

- The center has all the documents necessary for archiving
- All samples have been shipped to the appropriate laboratories
- All unused materials and products have been either destroyed or returned to the Sponsor

13.4.2 Audits and Inspections

A quality assurance audit may be performed at any time by the Sponsor's Clinical Quality Assessment department (CQA) or by independent auditors to verify that the study has been conducted according to the protocol, GCP and ICH requirements, and other applicable regulations. An inspection may be conducted by regulatory authorities. The Investigator must allow direct access to study documents during these inspections and audits.

13.4.3 Archiving

The Investigator and the study site shall retain and preserve 1 copy of the Study File containing the essential documents related to the study and records generated during the study ("Study File") for the longer of the 2 following periods ("Retention Period"):

- 25 years after the signature of the final study report or
- such longer period as required by applicable regulatory requirements

If during the Retention Period, the study site is no longer able to retain the Study File due to exceptional circumstances (such as bankruptcy), the study site shall contact the Sponsor to organize the transfer of the Study File to the Sponsor's designee at the Sponsor's expense.

Following the Retention Period, the Investigator and/or the study site are responsible to dispose of the Study File according to the applicable regulations. Patient medical records shall be retained in compliance with local regulations.

Archived data may be held on electronic records, provided that a back-up exists and that a hard copy can be obtained if required. The protocol, documentation, approvals, and all other documents related to the study will be kept by the Sponsor in the Trial Master File (TMF). Data on AEs are included in the TMF. All data and documents will be made available if requested by relevant authorities.

13.5 Financial Contract and Insurance Coverage

A Clinical Trial Agreement will be signed by all the parties involved in the study's performance, if relevant. The Sponsor has an insurance policy to cover any liabilities that may arise from use of the product and / or the study protocol.

13.6 Stipends for Participation

Subjects may be provided with a stipend according to local practice to compensate for their participation in the study (eg, dedicated time and travel required for study visits and procedures).

1.1	25 August 2021	
The SAP was amended after the first database lock and after the unblinding of the study for active phase (DBL#1, achieved on 28May2021), but prior to the final database lock (DBL#2).
 
The SAP was updated only to correct inadvertently truncations and unnecessary statements in previous version of SAP v1.0 dated 20APR2021. Actually, no modification was made compared to what were stated in Section 12.1.1.2 and Section 12.1.2.2 in the Protocol Amendment 2, dated 27APR2020. The changes have no impact on the first statistical analyses for active phase (DBL#1) and final analysis (DBL#2).
 
1) Section 5.1.1.2 Statistical Methods Fixed the statement in the last paragraph, which was not understandable, as inadvertently truncated in the former version. The following correction was made to keep consistency with protocol. The statement “Each non-inferiority will be demonstrated if the lower limit of the 95% CI of the difference of the proportion of subjects with an RVNA titer ≥ 0.5 IU/mL at D28 to 95% will be tested only if the primary objective is demonstrated.” was updated to “Each non-inferiority will be demonstrated if the lower limit of the 95% CI of the difference of the 2 proportions $P_{VRVg-2} - P_{control}$ is $> -5\%$ at D28.” Overall non-inferiority will be demonstrated if both of the non-inferiority between VRVg-2 + HRIG and Verorab vaccine + HRIG and between VRVg-2+HRIG and Imovax Rabies vaccine + HRIG are demonstrated at D28.”
 
2) Section 5.1.2.2 Statistical Methods Removed the paragraphs for the GM of individual titer ratio (GMTR) between two different time points on D14/D0, D28/D0 and D42/D0 within each group and

Previous Version(s)*	Date	Comments (optional)
		
the 95% CI from this section.
 
The methodology for GMT, GMTR and 95% CI was already mentioned and presented correctly in Table 5.1 and corresponding paragraph under Table 5.1
 
The following paragraphs were removed.
 
“The GM of individual titer ratio (GMTR) between two different time points on D14/D0, D28/D0 and D42/D0 within each group will be calculated, and 95% CI will be provided as follows.
 
Logarithm transformation of the individual titers will be calculated. Assuming that individual $\log_{10}(\text{titer})$ is normally distributed, the 95% CI for the difference in $\log_{10}(\text{GMT})$ between two time points will be in the form:
 $\bar{X}_1 - \bar{X}_2 \pm t(1 - \alpha/2, n_1 + n_2 - 2) \cdot S \sqrt{1/n_1 + 1/n_2}$ 
where $\bar{X}_i = \log_{10}(\text{GMT})$ is the mean of $\log_{10}(\text{titer})$ of time point i,
 
$S^2 = [(n_1 - 1) S_1^2 + (n_2 - 1) S_2^2] / (n_1 + n_2 - 2)$ is the pooled sample variance,
 
n_i and S_i^2 are the sample size and sample variance of time point i,
 
$t(1 - \alpha/2, n_1 + n_2 - 2)$ is the 100(1 - $\alpha/2$) percentile of the t-distribution with degrees of freedom $df = n_1 + n_2 - 2$.
 
The 95% CI for the GMTR between two time points will be formed by taking the same antilogarithms of the lower and upper limits of the 95% CI for the difference in $\log_{10}(\text{GMT})$ between two timepoints.”

Table of Contents

Version History	2
List of Tables	7
List of Abbreviations	8
1 Trial Objectives Introduction	10
2 Trial Objectives	10
2.1 Primary Objective	10
2.2 Secondary Objectives.....	11
2.3 Trial Plan.....	12
3 Endpoints and Assessment Methods	14
3.1 Primary Endpoints and Assessment Methods.....	14
3.2 Secondary Endpoints and Assessment Methods.....	14
3.3 Derived Endpoints: Calculation Methods	14
3.3.1 Safety	14
3.3.1.1 Solicited Reactions.....	15
3.3.1.1.1 Daily Intensity.....	15
3.3.1.1.2 Maximum Overall Intensity.....	16
3.3.1.1.3 Presence	16
3.3.1.1.4 Time of Onset	16
3.3.1.1.5 Number of Days of Occurrence During the Solicited Period	17
3.3.1.1.6 Overall Number of Days of Occurrence	17
3.3.1.1.7 Ongoing	17
3.3.1.2 Unsolicited AEs (Including SAE and AESI)	17
3.3.1.2.1 Presence	17
3.3.1.2.2 Intensity	17
3.3.1.2.3 Last Vaccination	18
3.3.1.2.4 Time of onset	18
3.3.1.2.5 Duration	18
3.3.1.2.6 Serious Adverse Events	19
3.3.1.2.7 Adverse Events of Special Interest	19
3.3.1.3 Other Safety Endpoints	19

HRIG	human rabies immunoglobulin
GMT	geometric mean of titers
GMTR	geometric mean of titer ratio
IM	intramuscular
IU	international unit
LLOQ	lower limit of quantitation
MA	memory aid
MD	missing data
MedDRA	Medical Dictionary for Regulatory Activities
mL	milliliter
NA	not applicable
PEP	post-exposure
PrEP	pre-exposure
PPAS	per-protocol analysis set
PT	preferred term
Q1; Q2; Q3	first quartile; second quartile (median); third quartile
RCDC	reverse cumulative distribution curve
RFFIT	Rapid Fluorescent Focus Inhibition test
RVNA	rabies virus neutralizing antibody

SAE	serious adverse event
SafAS	safety analysis set
SAP	statistical analysis plan
SD	standard deviation
SOC	system organ class (primary)
TLF	table(s), listing(s), and figure(s)
V	visit
VAC	vaccination
WHO	World Health Organization

1 Trial Objectives Introduction

Currently, Sanofi Pasteur has 2 rabies vaccines registered worldwide and available on the market: Imovax® Rabies and Verorab®. Imovax Rabies, a human diploid cell vaccine (HDCV), was first licensed in 1975. It is currently registered in 19 countries, including the US, Canada, Australia and 13 European countries. On the other hand, a purified Vero rabies vaccine (PVRV), was first licensed in France in 1985 under the commercial name of Verorab, and is extensively registered worldwide in 84 countries including 10 European countries but not in the US, Canada, and Australia. Both vaccines have a well-defined safety and immunogenicity profile.

In an effort to further improve the available rabies vaccines and optimize the manufacturing process and life cycle management, Sanofi Pasteur is developing a Purified Vero rabies vaccine – serum free (SF), henceforth referred to as VRVg.

VRVg is issued from the Wistar Rabies Pitman Moore/WI 38 1503-3M strain. VRVg is highly purified with very low residual DNA content (<100 pg per dose) and it is produced without raw material derived from human or animal origin, and without antibiotics. VRVg is compliant with standards set by the European Union Pharmacopoeia, the WHO, and the US FDA.

VRVg constitutes an improvement of Verorab [REDACTED]

[REDACTED]

[REDACTED]

VRVg development has been conducted through stepwise adjustments based on various regulatory, pharmaceutical, and /or clinical rationales. Two formulations referred to as VRVg-1 and VRVg-2, have been subsequently explored and tested in overall, 6 clinical studies. [REDACTED]

[REDACTED] Sanofi Pasteur made the decision to modify the initial formulation of VRVg-1 in order to ensure an enhanced vaccine immune response. Following the results with the second formulation and the acceptance of the health authorities to go to phase III, VRVg-2, next step consists of 2 Phase III non-inferiority studies which will compare VRVg-2 with the 2 rabies vaccines marketed by Sanofi Pasteur (Verorab and Imovax Rabies vaccines) in a simulated post-exposure (PEP) Essen (5-doses) regimen in adults (the present VRV13 trial) and in a pre-exposure (PrEP) regimen comprising adult and pediatric populations (VRV12).

2 Trial Objectives

2.1 Primary Objective

Immunogenicity

To demonstrate that VRVg-2 is non-inferior to Verorab and Imovax Rabies vaccines when co-administered with HRIG, in terms of proportion of subjects achieving a rabies virus neutralizing antibody RVNA titer ≥ 0.5 international unit per mini liter (IU/mL) at D28, ie, 14 days after the fourth vaccine injection.

2.2 Secondary Objectives

Safety

To describe the safety profile of VRVg-2 versus Verorab and Imovax Rabies vaccines when co-administered with HRIG, as well as that of VRVg-2, after each vaccine injection.

Immunogenicity

To demonstrate that the proportion of subjects in the VRVg-2 + HRIG group achieving an RVNA titer ≥ 0.5 IU/mL at D28 is at least 95%.

To describe the immune response induced by VRVg-2 versus Verorab and Imovax Rabies vaccines when co-administered with HRIG, as well as that induced by VRVg-2, at D14 (7 days after the third injection), at D28 (14 days after the fourth injection) and at D42 (14 days after the fifth injection).

Description of the Overall Trial Design and Plan

Trial Design

This will be a multi-center, modified double-blind (Groups 1 to 3)/open (Group 4), controlled, randomized, Phase III study in 636 subjects aged ≥ 18 years. Subjects will receive 5 vaccine injections of either VRVg-2 (Groups 1 and 4), Verorab vaccine (Group 2) or Imovax Rabies vaccine (Group 3), at day [D] 0, D3, D7, D14, and D28 (ESSEN regimen). All groups with the exception of Group 4 will additionally receive human rabies immunoglobulin (HRIG) at D0.

Vaccination and HRIG will be administered through the intramuscular (IM) route.

Subjects will be randomized 3:1:1:1 (Group 1, 2, 3, and 4, respectively) with the resulting number of subjects assigned to each study group shown in [Table 2.1](#).

Table 2.1: Distribution of subjects according to vaccination group

	Vaccine	Number of subjects
Group 1	VRVg-2 + HRIG	318
Group 2	Verorab® + HRIG	106
Group 3	Imovax® Rabies + HRIG	106
Group 4	VRVg-2	106

In case of any new study hold, withdrawn or out of vaccination time windows subjects might be replaced and sample size might be increased accordingly.

2.3 Trial Plan

The trial plan is summarized in [Table 2.2](#).

Table 2.2: Study procedures

Phase III Trial, 7 visits, 1 phone call, 5 vaccinations, 4 blood samples, 7 months period per subject

Visit	V01	V02	V03	V04	V05	V06	V07	Phone Call
Visit interval	VAC1	VAC2= VAC1+3D	VAC3 = VAC1+7D	VAC4 = VAC1+14D	VAC5= VAC1+28D	VAC5+14D	VAC5+28D	VAC5*+6M
Indicative Days (D)/Months (M)	D0	D3	D7 +1D	D14 ±1D	D28 ±3D	D42 ±3D	D56 ±3D	M7 +14D
Informed consent signed	√							
Demographic data	√							
Urine pregnancy test†	√	√	√	√	√			
Physical examination‡	√	√	√	√	√	√	√	
Past and current significant medical history	√							
Inclusion & exclusion criteria	√							
Randomization	√							
Blood sampling for serology (6 mL)	√			√	√	√		
Vaccine injection	√	√	√	√	√			
HRIG administration§	√							
30-minute observation period	√	√	√	√	√			
Diary Card (DC) Memory Aid (MA) Provided Checked Collected	DC1	DC1	DC1	DC2 DC1 DC1	DC3 DC2 DC2	DC3	MA DC3 DC3	MA
Injection site reactions and Systemic Event Assessment	√	√	√	√	√	√	√	
Temporary contraindications		√	√	√	√			
Definitive contraindications		√	√	√	√			
Reportable concomitant medication	√	√	√	√	√	√	√	
Termination Record							√	
Pregnancy cases	Collected throughout the entire study period							
SAEs and AESIs	Collected throughout the entire study period							

* VAC5 or last vaccine injection in the event of early terminated subject, contacted for the 6 months follow-up period through a phone call

†For subjects of childbearing potential

‡ Complete physical examination at V01 and medically-driven physical examination for remaining visits

§With the exception of subjects from Group 4 (who will receive VRVg-2 only)

Blood sampling

All subjects will provide blood samples before the first vaccination at D0 (baseline titer) and for the assessment of the immune response to the rabies vaccines at D14 (7 days after the third vaccine injection), D28 (14 days after the fourth vaccine injection), and D42 (14 days after the fifth vaccine injection).

Collection of safety data

Safety will be assessed in all subjects during the vaccination period and up to 28 days after vaccinations, in terms of occurrence of adverse events (AEs), serious adverse events (SAEs) and adverse events of special interest (AESIs). In addition, SAEs and AESIs will be collected up to 6 months after the last vaccination in all subjects.

3 Endpoints and Assessment Methods

3.1 Primary Endpoints and Assessment Methods

See Section 9.1 of the protocol.

3.2 Secondary Endpoints and Assessment Methods

See Section 9.2 of the protocol.

3.3 Derived Endpoints: Calculation Methods

3.3.1 Safety

Terms used in the standard safety tables to describe the safety events are specified below.

- AE: Adverse event includes solicited reaction and unsolicited event (including non-serious and serious adverse events).
- Adverse Reaction (AR): Corresponds to AE related to the study vaccine (investigational product), unless otherwise specified.
- Immediate: Unsolicited systemic AE checked “Yes” in the field of “immediate (within 30 minutes from the vaccination)” by the Investigator in the electronic case report form (eCRF).
- Solicited reaction: Event pre-listed in the eCRF, and which occurred during the solicited period (up to 7 days after the day of each vaccination).
- Unsolicited AE: AE recorded in the eCRF as unsolicited systemic event or unsolicited injection site reaction.
- Unsolicited injection site reactions are to be considered as related to the study vaccine injection and therefore will be analyzed as ARs.

Note: HRIG being an additional study medication (non-investigational product), any AEs occurring at HRIG injection location will be reported as unsolicited systemic events in this study.

- Unsolicited AEs will be analyzed up to 28 days after any and each vaccination. Unsolicited AEs occurring before or after the defined period will not be presented in the summary for unsolicited AEs but will be presented in a separate listing. The exceptions are SAEs and AESIs which are unsolicited AEs collected during the whole study period (after the first vaccination to end of 6 months safety follow-up period).
- SAE: Unsolicited AE considered serious by the Investigator (reconciled with Global Pharmacovigilance database).
- AESI: Is one of scientific and medical concern specific to the Sponsor's product or program, for which ongoing monitoring and rapid communication by the Investigator to the Sponsor can be appropriate. The Medical Dictionary for Regulatory Activities (MedDRA) preferred terms (PT) defined in the protocol are:
 - Anaphylactic reaction (PT)
 - Encephalitis (PT)
 - Convulsion (PT)

3.3.1.1 **Solicited Reactions**

3.3.1.1.1 **Daily Intensity**

All daily records for solicited reactions will be derived into daily intensity according to the following classification: None, Grade 1, Grade 2, Grade 3, or Missing (Unknown).

For the derivation of daily intensity, the following sequential steps will be applied:

- 1) For solicited reactions (except for fever) with an Investigator presence recorded as "No" in eCRF and with all daily records missing (unknown), and then all daily intensities will be derived as "None."
- 2) For a temperature partially missing after decimal point, the data will be analyzed replacing "MD" (missing data) by zero. For example, a "39.MD" daily temperature will be considered as "39.0°C" at the time of analysis.
- 3) For non-measurable solicited reactions, daily intensities will correspond to daily records reported in the clinical database. For measurable solicited reactions, the daily measurements reported in the clinical database will be converted based upon the intensity scales defined in the protocol; this assumes a reaction that is too large to measure (not measurable [NM]) is Grade 3. Note the intensity could be considered "None" (not a reaction) in the analysis despite being considered a reaction by the Investigator (eg, swelling measurement > 0 mm but < 25 mm).

Note: The maximum intensity on the ongoing period is derived from the record of the maximum intensity/measurement after the end of the solicited period following the rule described above.

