- General disorders and administration site conditions
 - Local reaction
 - Fever, chills
- Immune system disorders
 - Allergic type reaction
 - Anaphylactic shock
- Skin and subcutaneous system disorders
 - General pruritus
 - Rash

When medicinal products prepared from human blood or plasma are administered, the possibility of transmitting infective agents cannot be totally excluded despite strict control procedures and extraction/purification processes. This also applies to unknown or emerging viruses and other pathogens.

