6.4.2 Preparation and Administration

Imogam Rabies-HT is a ready-to-use, colorless to light opalescent solution for injection. The volume to be injected per subject is to be calculated based on the body weight (20 IU/kg) as presented as example in the table below.

Weight (kg)	Quantity of HRIG (IU)	Volume (mL)	Number of injections
60	1200	8	2
80	1600	10.67	3
100	2000	13.33	3
120	2400	16	4

A 5-mL syringe will be used and will be filled using several vials as necessary. The content of the syringe should be injected by the IM route at a body site distant from the rabies vaccine injection site (anterolateral thigh). A maximum of 5 mL is to be administered by injection; the total volume will be divided and administered at separate sites (sites should be at least 3 cm apart).

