A solicited reaction is an “expected” AR (sign or symptom) observed and reported under the conditions (nature and onset) prelisted in the protocol and CRB (eg, injection site pain or headache occurring between D0 and D7 post-vaccination).

By definition, solicited reactions are to be considered as being related to the product administered.

For injectable vaccines, solicited reactions can either be solicited injection site reactions or solicited systemic reactions.

The assessment of these reactions by the Investigator is mandatory.

Unsolicited AE / AR:

An unsolicited AE is an observed AE that does not fulfill the conditions prelisted in the CRB in terms of diagnosis and/or onset window post-vaccination. For example, if headache between D0 and D7 is a solicited reaction (ie, prelisted in the protocol and CRB), then a headache starting on D7 is a solicited reaction, whereas headache starting on D8 post-vaccination is an unsolicited AE. Unsolicited AEs includes both serious (SAEs) and non-serious unsolicited AEs.

Injection Site Reaction:

An injection site reaction is an AR at and around the injection site. Injection site reactions are commonly inflammatory reactions. They are considered to be related to the product administered.

Systemic AE:

Systemic AEs are all AEs that are not injection or administration site reactions. They therefore include systemic manifestations such as headache, fever, as well as localized or topical manifestations that are not associated with the vaccination or administration site (eg, erythema that is localized but that is not occurring at the injection site).

It is to note that the concomitant administration of vaccine and HRIG at D0 will not allow differentiation between systemic AEs related to the vaccine or to HRIG.

Adverse Event of Special Interest (AESI):

An AESI is one of scientific and medical concern specific to the Sponsor's product or program, for which ongoing monitoring and rapid communication by the Investigator to the Sponsor can be appropriate. Such an event might warrant further investigation in order to characterize and understand it. Depending on the nature of the event, rapid communication by the study Sponsor to other parties (eg, regulators) might also be warranted.

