4.3.2.2 Causality

By convention, all events reported at the study vaccine injection site (either solicited or unsolicited) will be considered as related to the study vaccine (investigational medicinal product) and then referred to as reactions.

In a same way, all solicited systemic events pre-listed in the CRF are also considered as related to study vaccination and will be considered as reactions.

For unsolicited systemic AE, missing relationship to the study vaccine (investigation product, including VRVg-2, Verorab and Imovax Rabies) in eCRF will be considered as related to study vaccine at the time of analysis.

Note: Due to the relationship to HRIG (non-investigation product) is not collected in eCRF, any AEs related to HRIG (including those occurring at HRIG injection location) will be reported as unsolicited systemic events and the relationship to HRIG will not be analyzed. In consequence, any AE considered as causally related to HRIG but not related to study vaccine will be analyzed as unsolicited systemic AE unrelated to study vaccine.

The missing relationship to study procedures for SAEs will not be imputed.

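### The SAP classes adverse events at the HRIG injection location as unsolicited systemic events, against the protocol's definition, and only groups given HRIG can have such events

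*SAP*

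**What the plan says.** Protocol Section 9.2.1.1 sets the definition: "Systemic AEs are all AEs that are not injection or administration site reactions". It lets a localized event count as systemic only when the event is not tied to the vaccination or administration site. SAP Section 3.2 refers to protocol Section 9.2 for the secondary endpoints and their assessment.

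SAP Section 3.3.1 then says that "any AEs occurring at HRIG injection location will be reported as unsolicited systemic events in this study", on the ground that HRIG is an additional, non-investigational product. SAP Section 4.3.2.2 repeats it: "any AEs related to HRIG (including those occurring at HRIG injection location) will be reported as unsolicited systemic events". Four other provisions matter here:

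- An unsolicited AE is an "AE recorded in the eCRF as unsolicited systemic event or unsolicited injection site reaction" (SAP 3.3.1). Those of the injection-site type are always analysed as related to the study vaccine.
- Relationship to HRIG is not collected. Under SAP 4.3.2.2, "any AE considered as causally related to HRIG but not related to study vaccine will be analyzed as unsolicited systemic AE unrelated" to the study vaccine, while a missing relationship "in eCRF will be considered as related to study vaccine at the time of analysis".
- Immediate AEs are unsolicited systemic AEs flagged as occurring within 30 minutes of vaccination (SAP 3.3.1).
- SAP Section 4.7, on changes to planned analyses, does not mention the reclassification.

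HRIG is given at D0 to Groups 1 to 3 and not to Group 4 (Protocol 5.1.1). Protocol 1.3.2 lists "Local reaction" among the post-marketing events for HRIG. Protocol 6.4.2 describes the administration: "A maximum of 5 mL is to be administered by injection; the total volume will be divided and administered at separate sites".

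**The concern.** A reaction confined to the thigh where HRIG was injected is an administration-site reaction. Under the protocol's definition it is not systemic; under the SAP it is. Following the SAP therefore places local events under a heading that the protocol says excludes them, and this can happen only in groups that received HRIG.

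What is at stake is the description of Group 4. Protocol Section 12.5 and SAP Section 4.5 say its results will be descriptive and set mainly against Group 1. A reader comparing all-cause unsolicited systemic AEs (after dose 1 and after any dose) or first-dose immediate AEs could take local thigh reactions for systemic effects of adding HRIG. Protocol 9.2.1.1 already concedes that true systemic effects of vaccine and HRIG cannot be told apart at D0. Thigh-site events can be told apart by location, so this part of the confounding is avoidable.

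**Working it through.** The plan states no figure for this point, so there is no rate to reproduce. The check is of the texts, of who can have such events, and of how the size depends on assumptions.

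**Texts.** The protocol wording covers the administration site as well as the injection site, and HRIG is described in protocol Section 6 (Products Administered) as Section 6.4. A narrow reading in which only the vaccine site counts does not fit.

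**Exposure.** Protocol 6.4.2 gives example volumes. Volume = 20 IU/kg × weight ÷ 150 IU/mL; number of injections = volume ÷ 5 mL, rounded up.

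- 60 kg: 1200 ÷ 150 = 8 mL, 2 injections
- 80 kg: 1600 ÷ 150 = 10.67 mL, 3 injections
- 100 kg: 2000 ÷ 150 = 13.33 mL, 3 injections
- 120 kg: 2400 ÷ 150 = 16 mL, 4 injections

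All four rows match the protocol's table. Local events are foreseeable, but no frequency is given.

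**Allocation.** Under SAP 4.2.3, a subject given VRVg-2 and HRIG at the first dose is analysed in Group 1, and a subject given VRVg-2 alone in Group 4. Group 4 therefore has no HRIG-site events by construction.

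**Size, all-cause rate.** Let s be the true unsolicited systemic AE rate, taken as equal in Groups 1 and 4, and h the HRIG-site AE rate, taken as independent of s. Both are assumptions. The reported Group 1 rate is 1 − (1 − s)(1 − h), so the excess over Group 4 is h(1 − s), in percentage points:

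| | h = 2% | h = 5% | h = 10% |
|---|---|---|---|
| s = 5% | 1.9 | 4.75 | 9.5 |
| s = 10% | 1.8 | 4.5 | 9.0 |
| s = 20% | 1.6 | 4.0 | 8.0 |

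At s = 20%, the extra Group 1 subjects number 318 × h × 0.80 = 5.1, 12.7 and 25.4.

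**Size, immediate AEs after dose 1.** With an assumed true rate of 1% and an assumed immediate thigh-site rate of 0.5%, 1% or 2%, the reported rate is 1 − 0.99 × (0.995, 0.99 or 0.98) = 1.5%, 2.0% or 3.0%.

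**Vaccine-related rate.** Let m be the share of thigh-site events with causality missing or attributed to the vaccine. With a true related rate of 10% and h = 5%, the excess is m × 0.05 × 0.90: 0 points at m = 0, 0.45 at m = 10% and 2.25 at m = 50%.

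**Group 1 versus Groups 2 and 3.** All three share h, so equal true rates stay equal. A true difference is only attenuated: with h = 10%, 20% versus 30% becomes 28% versus 37%, a gap of 9 points instead of 10.

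**The case against.** The case for leaving the rule alone has substance. The rule is stated openly, twice, with a reason. Keeping HRIG-site events out of the injection-site type is sound, because that type is automatically vaccine-related. The events are not spurious: they are consequences of the VRVg-2 + HRIG regimen. Safety is descriptive, and the planned tables by system organ class and preferred term would let a reader recognise some of them. All of this stands. It does not make a thigh reaction systemic, and the preferred-term tables cannot correct the subject-level overview or immediate counts.

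It is also fair that the secondary safety objective (Protocol 2.2) names no Group 1 versus Group 4 contrast, that Protocol 1.2 and 5.1.2 explain Group 4 by immune response, and that Group 4 is open-label. The comparison rests on the general statement in Protocol 12.5 and SAP 4.5, and it was never clean for subjective events.

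A reader might infer three stronger things that the documents do not support:

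- *That the rates are in fact raised.* A subject-level rate moves only if an HRIG-site event is reported, is not derived as no reaction (possible for redness or swelling below 25 mm under SAP 3.3.1.2.1 and 3.3.1.2.2), and occurs in a subject with no other unsolicited systemic AE in the period. The HRIG post-marketing list comes from voluntary reports, and the protocol says their frequency cannot always be reliably estimated. The immediate-AE part is weaker still, since Protocol 9.2.1.1 limits immediate events to medically relevant ones.
- *That the groups' confidence intervals would separate.* Nothing in the documents supplies the rates needed for that claim. In the assumed grid it happens only at h = 10% and s = 5%, by 0.12 points (10.79% versus 10.67%), and one subject either way removes it.
- *That the rule came in after unblinding.* The version history describes version 1.1 as correcting only two methods sections of version 1.0, dated 20 April 2021, before the lock of 28 May 2021.

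**Conclusion.** The SAP's classification contradicts the protocol definition, and the departure is not recorded. If HRIG-site events occur and are counted, they add to the all-cause unsolicited systemic AE rate, and possibly to the first-dose immediate AE rate, in Groups 1 to 3 and not in Group 4. The direction is known and the size is not: the range of 1.6 to 9.5 points rests entirely on assumed h of 2% to 10%, assumed s of 5% to 20%, independence, and equal s in Groups 1 and 4.

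The reach is limited. Comparisons of Group 1 with Groups 2 and 3 are not differentially biased. Solicited reactions and immunogenicity are untouched. Vaccine-related rates change only when causality is missing or attributed to the vaccine. The conditional Fisher test in SAP 4.1.3.1 is affected only if it is applied to an endpoint containing these events and involves the group without HRIG. This is a minor point of labelling and presentation.

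**What to change.** Keep these events out of the automatically vaccine-related injection-site category, but tabulate them as a separate HRIG administration-site category. At minimum, show unsolicited systemic AEs (after dose 1 and after any dose) and first-dose immediate AEs both with and without them.

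Identify the events from preferred and verbatim terms by a rule written before the tables are run, and keep the recorded causality. Label the tables supplementary and post hoc, since the active-phase data have been unblinded. Next to the note in SAP 3.3.1, and in SAP 4.7, state that the rule departs from the definition in protocol 9.2.1.1.

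The cost is a small term review, one extra table and a sentence in each place. Two limits remain: the review depends on how clearly the recorded terms show location, and separating these events removes neither true systemic effects of HRIG nor the open-label difference in Group 4.
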